Official Title: The Effect of a Gait Modification Training Program on Impact Loading and Running-related Injuries

NCT Number: NCT03302975

The Effect of a Gait Modification Training Program on Impact Loading and Running-related Injuries

Objectives

The purpose of this study is to determine whether a gait modification training program can result in a reduction in impact loading and the incidence of running-related injuries (RRI) among recreational distance runners. Knee angle at initial contact (IC) has been identified in a previous study by the principal investigator (pre-submission stage) as both increasing the average vertical loading rate (AVLR) and the incidence of RRI in the female recreational running population. This variable will be modified to determine the effect on impact loading (AVLR) and incidence of RRI using a repeated measures design.

Background

Numerous studies have shown that individuals can be trained to modify aspects of walking and running[1-18]. Moreover, gait retraining has been shown to be effective in treating overuse injuries in runners[4,7,8,18]. However, since it is unclear what variables independently contribute to the recovery from these injuries and whether these variables can be manipulated prospectively to reduce the risk of injury, optimal prevention and treatment of RRI remains unknown. These studies all included some form of feedback to the subjects, which helped them modify their technique. The feedback methods included verbal instructions and real-time visual[1,3,6,7,9,12,17,18] or auditory information[4,5,8,11,15,16]. Other studies used verbal instructions and videotape reviews[13,14] or an extensive training program[8,19]. Many of these studies have used

overlapping instructions and feedback which make it difficult to infer which factors had a causative effect on changing gait mechanics, muscle activation patterns, and ground reaction forces. Others have used feedback that is difficult to reproduce outside of a lab or clinic environment. Simple cues that produce a specific and intended kinematic or spatiotemporal modification are necessary. Furthermore, these cues need to be consistent and reproducible in multiple training environments in order to be retained as part of the motor program.

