Arendse et al[19] reported that 7.5 hours of training over 5 consecutive days was required to learn FF landing, while Dallam et al[20] reported a 1-hour session for 12 weeks was necessary. Diebal et al showed FF landing could be trained in 6 weeks, with training sessions 3 times per week for 45 minutes[8]. An 8-session faded-feedback approach was used by Barrios et al to retrain walkers. This design produced changes in lower extremity biomechanical variables immediately post-intervention as well as at 1-month follow-up [1]. Subjects who receive intermittent feedback have been shown to perform better in the long-term than subjects who receive continuous immediate feedback[21,22]. Removing the feedback is beneficial to motor skill learning because the subjects must rely on internal cues for performing correct motor patterns[23].

Some researchers have suggested that further studies should investigate the effect of gait retraining on injury prevention in runners[8,19]. Changing a runner's gait to reduce the risk of a certain injury, however, may have unintended consequences such as increasing the chance of another kind of injury if other kinematic or spatiotemporal variables are adversely impacted[2,19]. Knowledge of the independent contributions of identified kinematic and spatiotemporal risk factors to impact loading and injury

incidence will allow for targeted modification of these variables so that the risk of negative consequences is limited.

Hypotheses

It is hypothesized that after a 15-week training program, a change in knee flexion at IC will be significant ($p < 0.05$) and will result in decreased impact loading (AVLR) and incidence of RRI.

Outcome Measures

Primary outcome measures:

- 1) Kinetic outcomes: Average vertical loading rate (Body weights [BW] per second) and vertical impact peak (BWs).
- 2) Incidence of RRI (calculated as the number of new injuries reported per 100 runners at risk).

Secondary outcome measures:

Secondary outcome measures will be kinematic and/or spatiotemporal correlates of impact loading and incidence of RRI as guided by the literature and determined in previous studies.

- 1) Knee flexion angle at IC
- 2) Peak knee flexion angle
- 3) Angle of the shank at IC

Other outcome measures:

Other outcome measures will be collected to describe and assess the success of the gait modification intervention. These measures include:

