- 1) Participant compliance: Participant compliance with the gait modification intervention will be measured by the number of training sessions attended at Fortius (to a maximum of 8, converted to a percentage) and the number of home training sessions completed (to a maximum of 22, converted to a percentage). Participants will record their home training sessions in their weekly online questionnaire.
- 2) Adverse events: Adverse events experienced due to the intervention (i.e. increased pain or a new injury) will be recorded in the weekly online questionnaires.
- 3) Fidelity of training sessions: Assessed by calculating the difference (error, in degrees) between the intended target angle and the actual angle produced during the 10 consecutive stance phases at each of the four time points during each training session (first min, 33%, 66%, and last min) and averaged within the session.
- 4) Perceived difficulty in achieving targeted modification: Assessed at each training session using an 11-point numerical rating scale (NRS) (0 = “no difficulty”, 10 = “unable to perform”).
- 5) Pain: Assessed at each training session using an 11-point NRS (0 = “no pain”, 10 = “worst pain imaginable”).
- 6) Rating of Perceived Exertion (RPE): Assessed at each training session using the 15-point Borg RPE scale.

- 7) Anthropometric and functional measurements: These will include BMI, navicular height, hip internal/external rotation range of motion, Q-angle, and weight-bearing ankle dorsiflexion and knee valgus angle.

Methods

The proposed study is a repeated measures design. A sample size calculation for comparing injury incidence is based on our current injury rate (27.9%) in our previous studies. We calculate that we will require a sample size of 30 to achieve a minimum power of 80% ($\alpha = 0.05$). Thirty uninjured female recreational runners will be recruited through advertisements in Vancouver-area running clinics. Participants must be female between the ages of 18 and 60; have been running for at least three months prior to study commencement; and have experience with running on a treadmill. Participants must not have run more than two half marathons previously. Participants will be excluded if they have experienced a lower extremity injury in the prior three months; have undergone hip, knee, or ankle joint surgery; or currently have pain in their lower back or lower extremities while running.

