Pain, RPE, and perceived difficulty in achieving the targeted modification will be measured in all training sessions using an 11-point NRS (pain and perceived difficulty) and the Borg RPE scale. Adverse events (increased pain or a new injury) and participant compliance with the gait intervention will be assessed in the weekly online questionnaire.

All participants will return to the Fortius Biomechanics Lab at the conclusion of the 15-week half-marathon clinic for retesting. A one-month post-test will also be performed to assess for retention. During both sessions (follow-up and retention), the participants will be asked to run naturally and then with the modified pattern. The natural pattern will be collected to determine whether it has changed since baseline.

The verbal instruction during each training session will be given by the principal investigator (a sport physiotherapist with clinical experience in gait retraining). The therapist will not be involved in data collection, but will process the data. To ensure blinding, data will be collected by an independent lab assistant and coded to blind for participant number for later processing and analysis by the principal investigator. This process will ensure that the principal investigator is unaware of which participant they are analyzing until the conclusion of the study.

Demographic, anthropometric, and functional variables will be analyzed for differences between the intervention group and a historical control group from our previous studies at baseline using 2-tailed t-tests for normally distributed continuous variables. Injury incidence (number of new injuries reported per 100 runners at risk) will be compared between groups using paired t-tests. Differences in outcomes pertaining to the feasibility of the intervention (perceived difficulty, exertion, fidelity, compliance) will

be assessed in the intervention group between session 1 and 8 using paired t-tests. The biomechanical and clinical outcomes from the follow-up and one-month post-intervention modified patterns will be compared to the baseline values using ANOVAs for repeated measures. Planned pairwise comparisons between the visits will be conducted. Differences will be considered statistically significant at $p < 0.05$. All statistical analyses will be performed using SPSS version 22.0 (SPSS Inc., Chicago, IL).

References

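### The plan has no rule for missed visits; if its three-visit repeated-measures ANOVA is run on complete cases, a runner who misses only the one-month visit also leaves the end-of-training comparison

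*Combined protocol and SAP*

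**What the plan says.** The final Methods paragraph states that the biomechanical and clinical outcomes "from the follow-up and one-month post-intervention modified patterns will be compared to the baseline values using ANOVAs for repeated measures". It adds: "Planned pairwise comparisons between the visits will be conducted". It names SPSS 22.0 but no procedure, and it does not say whether the pairwise comparisons come from the ANOVA or are separate paired tests.

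The visits are described earlier in Methods: "All participants will return to the Fortius Biomechanics Lab at the conclusion of the 15-week half-marathon clinic for retesting", and "A one-month post-test will also be performed to assess for retention". At both, "the participants will be asked to run naturally and then with the modified pattern". The document gives no analysis population, no rule for a missed visit and no imputation or mixed model. It does not say whether injured runners are retested. Methods recruits exactly the 30 runners that it calculates are required.

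**The concern.** A conventional repeated-measures ANOVA over three visits needs a complete row for each runner. The retention visit therefore decides who counts in the end-of-training comparison, which concerns the primary kinetic outcomes. Two things are at stake.

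- **Precision.** Recorded pairs of values are discarded in a study of 30 with no spare recruitment.
- **Bias.** If the runners who miss the last visit differ in average vertical loading rate (AVLR), the completers' change is distorted, in a direction that cannot be known beforehand.

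Some informative loss is plausible. The sample size is "based on our current injury rate (27.9%) in our previous studies", so injuries are expected. Objectives describes the screened knee angle as "both increasing the average vertical loading rate (AVLR) and the incidence of RRI".

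**Working it through.** **Inputs.** From the document: 30 runners, three test visits, significance level 0.05, 80% power. Assumed: a two-sided test, and the number, pattern and causes of missed visits, because the document gives none. The plan has no figure of its own to reproduce here: its 30 is calculated for injury incidence.

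**Step 1: does the method drop the runner?** With 6 of 30 one-month values removed from a trial dataset, a standard repeated-measures ANOVA routine would run only on the 24 complete runners (error df 2 × 23 = 46 instead of 2 × 29 = 58). All 30 had baseline and end-of-training values.

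**Step 2: precision.** The end-of-training contrast is a paired comparison. Its power comes from the noncentral t distribution with n - 1 df and noncentrality d√n, where d is the change divided by the SD of the paired difference.

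- n = 30: 80% power at d = 0.529.
- 10% lost: 30 - 3 = 27. Power for d = 0.529 is 75%; the standard error rises by √(30/27) = 1.05.
- 28% lost: 0.279 × 30 = 8.4, so 30 - 8 = 22. Power is 66%; the standard error rises by √(30/22) = 1.17.

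The change detectable with 80% power is 0.53, 0.57 and 0.63 SDs of the paired difference at n = 30, 26 and 22.

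**Step 3: bias among completers.** Simulation with 30 runners and no true change. Loss of the one-month visit follows a logistic function of end-of-training AVLR, with higher values more likely to be lost. The odds ratio per SD is e^0.5 ≈ 1.6 (weak) or e^1.5 ≈ 4.5 (strong).

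The biases are in SDs of the outcome, a different unit from step 2. The SD of the difference is √(2(1 - r)) outcome SDs, where r is the baseline-to-end correlation. The detectable change at n = 30 is converted in the third column.

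| r | SD of difference | Detectable change, outcome SD | Bias, 10% lost, strong | Bias, 28% lost, weak | Bias, 28% lost, strong | False positives, 28% lost, strong |
|---|---|---|---|---|---|---|
| 0.30 | 1.18 | 0.63 | -0.086 | -0.100 | -0.218 | 13.2% |
| 0.50 | 1.00 | 0.53 | -0.066 | -0.073 | -0.154 | 11.0% |
| 0.70 | 0.77 | 0.41 | -0.035 | -0.039 | -0.091 | 7.6% |
| 0.85 | 0.55 | 0.29 | -0.019 | -0.022 | -0.047 | 6.9% |

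With 10% lost and weak dependence the bias is 0.01-0.04. At 10% loss, false positives stay at about 5-6%. A negative bias looks like a reduction in loading. If loss follows the baseline value instead, the sizes are the same and the sign is positive.

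**Step 4: the alternative.** With 28% missing only the one-month visit, a mixed model with unstructured covariance gives the same end-of-training contrast as the paired test on all 30, with false positives of 4.4-5.9%. Its one-month contrast is within 0.01 SD of zero when loss follows a recorded value, with false positives of 5.2-7.2%, so slightly high. These figures rest on 4,000 simulated studies per setting.

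**The case against.** **The harm is doubly conditional.** It needs a complete-case ANOVA that also supplies the contrasts, and runners who miss only the last visit. A reader might infer that the plan will discard these runners. It does not say so: separate paired tests would keep them in the end-of-training contrast. This stands, and it limits the claim to what happens under the conventional reading. Separate paired tests would still not repair the one-month contrast, or either contrast when both post-training visits are missed.

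**27.9% is not a loss rate.** A reader might infer that about 28% will be lost. The figure is an injury rate from earlier studies, and this study hypothesises fewer injuries. It serves only as an upper illustration; at 10% loss the bias is small.

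**The link to AVLR is indirect.** The document ties knee angle to loading and injury, but enrols only runners below 10° of knee flexion. It does not show that AVLR predicts injury or loss within that group, so informative loss remains an assumption.

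**Injury may cost other visits.** An injury during training could as well cost both post-training visits. If these are lost according to the unrecorded end value at 28% loss, the mixed model is more biased than completers: 0.10-0.28 against 0.05-0.22 outcome SD under strong dependence, and 0.04-0.12 against 0.02-0.10 under weak. This stands as a real cost of the fix.

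**Vertical impact peak.** A reader might also infer that nothing covers an absent peak. Methods does give a rule that keeps AVLR computable for every runner (initial contact to 13% of stance). Only the peak itself, as a primary outcome, has no stated handling when absent. That is a minor clarification with no measurable size here.

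**Conclusion.** The concern holds in conditional form. The stated method has no missed-visit rule, and in its conventional form it discards recorded baseline and end-of-training pairs. The loss of power follows directly from the number lost: about 75% if 3 of 30 miss the one-month visit, about 66% if 8 do.

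The bias further assumes that loss depends on recorded AVLR. It is 0.01-0.09 outcome SD at 10% loss and 0.02-0.22 at 28%, with false positives of about 5-6% and 5-13%. In the worst setting shown, bias is 0.218/0.63, about 35% of the detectable change. In the strong 10% settings it is about 7% (0.019/0.29) to 14% (0.086/0.63).

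The documents do not support a statement that the result will be biased, or in which direction. The change is worth making because it is cheap and settles the choice before the data are seen.

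**What to change.** Replace the ANOVA sentence in the last Methods paragraph with:

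> The biomechanical and clinical outcomes will be analysed with a mixed model for repeated measures using every recorded value from the three test visits (baseline, end of training and one month; modified pattern at the two post-training visits; training-session data not included), with visit as fixed factor, unstructured within-runner covariance, REML and Satterthwaite or Kenward-Roger degrees of freedom, and planned contrasts of each post-training visit against baseline. Missed visits and reasons will be reported, and a completers-only analysis given as sensitivity.

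The text names the modified pattern because both patterns are recorded after training. It excludes training-session data because kinetic data are also collected at the eight lab sessions. A random intercept alone should not replace the unstructured covariance, because the two modified-pattern visits may correlate more with each other than with baseline. With correlations of 0.3 (baseline to post-training) and 0.9 (between the post-training visits), and 28% strongly dependent loss, it gave end-of-training false positives of 9.8% and a one-month bias of -0.157 SD.

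**Cost.** Analysis wording only, with no new data. The model assumes that loss depends on recorded values. Besides the case of both visits lost, if loss of the one-month visit follows an unrecorded stable level, its one-month change is off by 0.01-0.09 SD at 28% loss, while completers are near zero. The reported reasons and the completers-only analysis are there for this.

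Separately, and as a clarification only, the sponsor could state how a missing vertical impact peak is handled.

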Using an eight-camera passive marker system (Qualisys Motion Capture Corp., Gothenburg, Sweden) and Visual 3D software (C-Motion, Inc., Germantown, MD), participants will undergo a static calibration trial to form a musculoskeletal model. Anthropometric properties of body segments will be scaled to each individual using the subject's height, mass, and segment lengths. Each model segment position will be multiplied by the respective mass; these numbers will then be summed and divided by the total body mass. For bilateral analysis, 19 static/calibration markers and 42 tracking markers (total = 61) will be affixed to each subject. Before data collection, each subject will be allowed 5 minutes to warm-up and determine their speed. Participants will be able to adjust the speed as needed over this period until they identify a speed that is representative of a typical moderate intensity run. Participants will then be asked to identify their rating of perceived exertion (RPE) using Borg's RPE scale [33]. The speed will be adjusted until the participant is at an RPE of 13 ("Somewhat hard" or 70% effort). Three-dimensional kinematic and spatiotemporal data will be collected at this pace over three trials of 15 seconds using the six-camera, three-dimensional motion analysis system. Kinetic data will be collected using an embedded force platform in the instrumented treadmill. All kinetic variables will be normalized to subject body mass. Initial contact and toe-off will be identified by force plate data (using a threshold of 50N).

These data points will be used to determine the stance and swing phases of the gait cycle. All outcome measures will be determined by averaging the first 10 consecutive stance phases within each of the three trials ($n = 30$ total stance phases). For the purposes of comparison between RF strikers and MF/FF strikers (who may not display a clear VIP), AVLR will be calculated for all individuals as the slope of the vertical GRF–time curve from IC to 13% of stance. This time value has been shown to be the best surrogate for the timing of a missing VIP.

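### Three primary outcomes are each tested at p < 0.05 with no lead outcome, primary contrast or multiplicity rule; the chance of a false-positive primary result is about 12–14%, and up to about 27% if every visit contrast is tested

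*Combined protocol and SAP*

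**What the plan says.** The Outcome Measures section has two numbered primary items that hold three variables. The first is "Kinetic outcomes: Average vertical loading rate (Body weights [BW] per second) and vertical impact peak (BWs". The second is "Incidence of RRI (calculated as the number of new injuries reported per 100 runners at risk".

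The last paragraph of Methods sets out the tests. Injury incidence "will be compared between groups using paired t-tests". For the biomechanical outcomes, the "follow-up and one-month post-intervention modified patterns will be compared to the baseline values using ANOVAs for repeated measures". It then adds "Planned pairwise comparisons between the visits will be conducted", without saying which pairs or whether they depend on the ANOVA result. The only decision criterion is "Differences will be considered statistically significant at $p < 0.05".

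Two other places bear on the point. The Hypotheses section predicts a fall in AVLR and in RRI incidence once the 15-week programme is complete; it does not mention vertical impact peak. The treadmill-testing part of Methods refers to "MF/FF strikers (who may not display a clear VIP", and gives a substitute time point (13% of stance) for computing AVLR in such runners.

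**The concern.** With three primary outcomes and one unadjusted threshold, a significant result on any one of them can be presented as a positive primary finding. The visit comparisons widen the choice: each kinetic outcome can be read at the end of training, at one month, or both. Nothing fixes in advance which result decides the trial, so the nominal 5% does not describe the chance of at least one false-positive primary result. A reader of the final report could not tell a prespecified lead result from one picked after the data were seen.

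**Working it through.** **The plan's own figure.** The document gives no family-wise error rate, so there is none to reproduce. Its sample size (30, from an injury rate of 27.9%) concerns injury incidence only and does not enter the multiplicity calculation except as n.

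**Inputs from the document**
- Level per test: 0.05 (Methods, statistical paragraph). Two-sided is assumed for the outcomes; the plan says two-tailed only for the baseline group comparisons.
- Kinetic primary outcomes: 2. Injury outcome: 1, with one between-group test.
- Visits for the kinetic outcomes: 3 (baseline, 15-week retest, one month).
- n = 30.

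**How many primary tests.** The number of visit contrasts is not stated, so three counts are possible:
- one contrast per kinetic outcome: 2 × 1 + 1 = 3
- both post-training visits against baseline: 2 × 2 + 1 = 5
- all visit pairs: 2 × 3 + 1 = 7

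**Ceiling under independence**, 1 − 0.95^k:
- k = 3: 1 − 0.95³ = 14.3%
- k = 5: 1 − 0.95⁵ = 22.6%
- k = 7: 1 − 0.95⁷ = 30.2%

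**Allowing for dependence.** The tests are not independent. Among three visits, any two differences fix the third. If the visits have equal variance σ² and equal correlation ρ, each difference has variance 2σ²(1 − ρ), and two differences that share a visit have covariance σ²(1 − ρ) in absolute value, so their correlation is ±0.5 whatever ρ is. The two kinetic outcomes are probably correlated as well, by an amount the document does not give.

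A simulation under the global null covers both features: n = 30, three visits, paired t-tests, an injury test that is independent of the kinetic tests and holds 5%, and 20,000 runs per setting. The visit correlation (0.6) and the outcome correlations are assumptions. Chance of at least one p < 0.05:

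| Tests | Outcome correlation 0 | 0.5 | 0.9 |
|---|---|---|---|
| 3 (one contrast each) | 14.3% | 13.6% | 11.7% |
| 5 (both visits against baseline) | 21.7% | 20.1% | 17.1% |
| 7 (all pairs, ungated) | 27.2% | 25.2% | 21.2% |
| All pairs, only after a significant ANOVA | 14.5% | 13.6% | 11.4% |

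The simulation standard error is about √(0.13 × 0.87 / 20,000) = 0.24 percentage points for rates near 13%. A repeat over correlations 0 to 0.9 gave 12–14%, 17–22%, 21–27% and 12–15% for the four rows.

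**Effect of the two possible rules for AVLR and injury**
- Both required at 0.05: the chance that both are false positives is 0.05 × 0.05 = 0.25% if the tests are independent, and cannot exceed 5% under any dependence.
- Holm: the smaller p-value is compared with 0.05 / 2 = 0.025, then the larger with 0.05. The family-wise rate is at most 5%.

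**The case against.** Several points on the other side have force.

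- **The hypothesis already points to AVLR after 15 weeks, together with injury.** That is its natural reading, and the sample size rests on injury alone. But the hypothesis is a prediction. It is not written as a success criterion, it leaves out an outcome that is listed as primary, and the analysis text does not refer back to it.
- **The ANOVA may act as a gate.** If pairwise tests follow only a significant ANOVA, the visit contrasts add almost nothing and the rate is about 12–15%. The plan does not state this gate, and the rate would still be more than double 5%.
- **Retention is not benefit.** A reader might infer that any of seven results could be claimed as a treatment effect. The document does not support that: the one-month visit is there to assess retention, and a difference between 15 weeks and one month is not evidence of improvement over baseline. Five tests are therefore the more relevant count if both visits are tested.
- **Direction.** The hypothesis predicts decreases, so half of the two-sided false positives on a single test would point the wrong way. Counting only false claims of benefit, three independent tests give 1 − 0.975³ = 7.3% against 2.5% for one test. Allowing for correlation, the rate is about 6–7% for three tests and 8–11% for five. The absolute figures fall, but the ratio to the single-test rate stays at two and a half or more.
- **All nulls true.** The percentages need this, whereas the sponsor's premise is that knee angle at contact affects AVLR. They also need the injury test to hold its 5% level, which is doubtful for a paired t-test on injury incidence. Both are conditions on the size; neither supplies the missing decision rule.

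**Conclusion.** The point stands. Three primary outcomes share one unadjusted threshold, and no lead outcome, primary contrast, both-required rule or adjustment is written. The chance of at least one false-positive primary result, two-sided, is about 12–14% with one contrast per kinetic outcome (12–15% if pairwise tests follow a significant ANOVA), about 17–22% with both post-training visits tested against baseline, and up to about 27% with all pairs ungated. These figures assume that all nulls are true, that each test holds 5%, that the injury test is independent of the kinetic tests, and that the correlations are as stated above.

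Two stronger readings should not be drawn. A reader might quote 30% for seven tests; that is the independence ceiling, and three linearly dependent visit contrasts do not reach it. A reader might also attribute the inflation to having 30 runners and a historical control group. Those features raise separate questions, but they do not cause this error rate; the number of tests and the absence of a rule do.

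**What to change.** Amend the statistical paragraph and the outcome list before the data are analysed:

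1. Name AVLR, baseline versus the 15-week retest, as the single primary kinetic contrast. This is the outcome and time that the hypothesis already uses.
2. Move vertical impact peak to the secondary outcomes. It is not in the hypothesis, and the plan itself expects that some runners may not show it.
3. State one rule for AVLR and RRI incidence: either both must succeed at 0.05, or the two are tested by Holm.
4. Label the one-month contrast and all remaining pairwise contrasts as secondary.

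No new data, visits or participants are needed. The costs are these. Under Holm, the smaller of the two p-values must be at or below 0.025. Under the both-required rule no alpha is lost, but one positive outcome alone is not success. In either case one listed primary outcome is demoted, which is a change to the outcome list and should be recorded as such.
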